#### **ABSORB IV Secondary Objectives:**

- To evaluate 1-year clinical outcomes of the Absorb BVS compared to XIENCE in the treatment of subjects with ischemic heart disease caused by up to three *de novo* native coronary artery lesions in a maximum of two epicardial vessels, with a maximum of two lesions per epicardial
- To evaluate the incidence of angina occurring within 1 year with treatment of Absorb BVS compared to XIENCE.

### **4. CLINICAL TRIAL/INVESTIGATION FLOW AND FOLLOW-UP SCHEDULE**

#### **4.1 Number of Subjects to be Registered**

Approximately 2600 subjects will be registered in ABSORB IV from approximately 140 sites in the United States and outside the United States. The enrollment/registration of ABSORB IV will start after the completion of enrollment/registration of the 2000 primary analysis subjects of ABSORB III.

#### **4.2 ABSORB Physician Training**

[figure not shown]
Investigators that have not participated in previous ABSORB trials or are not commercial users of the Absorb BVS device will participate in the ABSORB IV physician training program. Please refer to **section 4.2** of ABSORB III Protocol (Version 17.0, August 09, 2018) for the detailed information on the didactic training.

#### **4.3 ABSORB IV Treatment Flow and Lesion Selection**

A maximum of three *de novo* native coronary artery lesions will be treated in a maximum of two epicardial vessels, with a maximum of two lesions per epicardial vessel. If there are two target lesions within the same epicardial vessel, the two target lesions must be at least 15 mm apart. One planned non-target lesion is allowed in ABSORB IV treated with a XIENCE per the IFU. However, in situations where treatment of a target lesion reveals additional lesion(s), the investigator may treat the lesion(s). This is considered an unplanned lesion. If the lesion meets enrollment criteria both before and after pre-dilatation, the lesion must be treated with the assigned device and will be considered to be an unplanned target lesion. If the lesion does not

meet the enrollment criteria (either before or after pre-dilatation), the lesion must be treated with XIENCE. This lesion will be considered as an unplanned non-target lesion.

**Figure 4.1** shows the lesion treatment for subjects in ABSORB IV.

**Figure 4.1** Lesion Treatment

Every attempt should be made that the two or three target lesion treatments occur at the same index procedure. However, if a staged procedure becomes necessary (e.g. due to high use of contrast or radiation after treatment of the first lesion), it is strongly recommended that the staged procedure occurs within 2 weeks of the index procedure using the assigned device, but in all cases no more than 35 days from the index procedure. To avoid having to cross a previously implanted study device, it is strongly recommended that the staged lesion(s) be located in a separate epicardial vessel from the lesion(s) previously treated during the first intervention. A maximum of one staged procedure is allowed. Staged procedures must only include target lesions identified at the time of the index procedure.

Prior to treatment with the assigned device (Absorb BVS or XIENCE), vessel sizing by visual estimation must be conducted to appropriately match the device to the size of the vessel. Quantitative methods such as on-line QCA, IVUS or OCT may be used if the site is experienced with these techniques. Specifically, use of pre-PCI and post-PCI IVUS or OCT is strongly

recommended to optimize device sizing results. Details on the vessel sizing methods can be found in **Imaging Guidance Document**.

To exclude enrollment of excessively small vessels, if the operator believes that based on visual angiographic assessments, the distal reference vessel diameter is  $\leq 2.75$  mm such that the plan is to implant a 2.5 mm device (stent or scaffold) in a target lesion, it is strongly recommended that either on-line QCA or intravascular imaging (ultrasound or optical coherence tomography) is used and demonstrates that the measured distal RVD for this target lesion is  $\geq 2.50$  mm (by at least one of these imaging modalities). This measurement may be performed before or after pre-dilatation, but before randomization. If the distal RVD measures  $<2.5$  mm, that lesion IS NOT ELIGIBLE for randomization. Such a lesion may be treated as a non-target lesion. **Table 4.1** provides the device sizes, RVD and lesion length for ABSORB IV.

**Table 4.1 Absorb BVS and XIENCE Sizes**

Device	Lesion and Device Sizes	
	RVD 	Lesion Length 
Absorb BVS (Target lesion)	RVD $\geq 2.50$ mm - $\leq 3.75$ mm Scaffold diameter: 2.5, 3.0 and 3.5 mm	Lesion length $\leq 24$ mm Scaffold Length  : 8, 12, 18 and 28 mm 
XIENCE  (Target lesion)	RVD $\geq 2.50$ mm - $\leq 3.75$ mm Stent diameter: 2.5, 2.75, 3.0, 3.25 3.5, 4.0 mm	Lesion length $\leq 24$ mm Stent Length: 8, 12, 15, 18, 23 and 28 mm 

 Reference vessel diameter (RVD) and lesion length based on visual estimation

 Both the 8 mm and 12 mm lengths will be available for the 2.5/3.0 diameter Absorb BVS. Only the 12 mm length will be available for the 3.5 mm diameter.

 For target lesion, planned overlapping is not allowed (i.e., the lesion must be eligible for treatment with a single stent). However, bailout overlapping is allowed if required.

 XIENCE V, XIENCE Prime, XIENCE Xpedition, XIENCE Alpine, XIENCE Pro, and XIENCE ProX will be used in this study.

The commercially approved CE marked 23mm Absorb BVS device will not be used in this study.

It is highly recommended a minimum of 2 mm (by visual estimation) of minimally diseased tissue be covered by the device at both the proximal and distal edges.

Planned overlap of the target lesion is not allowed. Overlap in the case of bailout is allowed. Please refer to **Section 7.3.5** for details regarding bailout.

#### **4.4 Measures Taken to Avoid and Minimize Bias**

In ABSORB IV there will be several measures taken to avoid and minimize bias such as randomization and blinding. This process is detailed in the following sections.

##### **4.4.1 Randomization**

###### **Stratified Randomization:**

Approximately 2600 subjects will be randomized 1:1 in the ABSORB IV trial (test device: Absorb BVS vs. control device: XIENCE). Randomization will be stratified by diabetes mellitus (diabetic vs. non-diabetic) and ABSORB III-like or not. ABSORB III-like will be determined by

**Confidential and Proprietary**

**Do not distribute or reproduce without the prior written permission of Abbott Vascular Inc.**  
**ABSORB III Randomized Control Trial Version 17.0 August 16, 2018.**

the absence of planned staged procedure, number of target lesions  $\leq 2$ , and no biomarker positive ACS or STEMI. Subjects will also be stratified by site at pre-specified expected high-enrolling sites. Other sites will be combined to ensure a sufficient number of subjects for the attainment of the desired randomization ratio. A centralized randomization service, IVRS, will be used.

### **Timing of Randomization:**

Randomization will be done after successful and uncomplicated pre-dilatation of at least one target lesion and vessel sizing (refer to **Protocol Summary**, Treatment Strategy, for details). If there is a non-target lesion, it must be successfully treated prior to randomization. If there are two or three target lesions, after the first target lesion was successfully pre-dilated and vessel sizing criteria still met, the operator may at this point choose to randomize the patient, or pre-dilate other lesions. If other lesions are pre-dilated, all such pre-dilatations must be considered successful according to the above criteria prior to randomization. If there are two target lesions in a single epicardial coronary artery, it is strongly recommended that both be successfully pre-dilated before the patient is randomized.

Once randomization is completed and a treatment is assigned, the assigned device must be used for all lesions. An Absorb BVS scaffold may never be used in a patient randomized to XIENCE. However, if the patient is randomized to Absorb BVS and the scaffold cannot be delivered or a complication otherwise develops that requires treatment with a drug-eluting stent, a XIENCE stent must be used. If the XIENCE stent is unable to successfully treat the patient, any commercially available device approved for use in that geography may be used as necessary in the best interests of the patient. Regardless of the actual device the subject received, the subject will be included in ITT population per the original randomization assignment.

The subject is considered to be successfully registered in this study and considered in the ITT population at the point of randomization (refer to Section 6.4). Refer to **Appendix IV (Figure 1 and 2)** for enrollment and registration timeline and flow chart.

#### **4.4.2 Blinding**

This is a single-blinded clinical trial. Subjects will be blinded to their treatment assignment and the study site personnel will be trained not to disclose the treatment assignment to the subject. In addition to standard procedural sedation, headphones will be worn by the patient during the procedure to reduce the possibility of unblinding. Additionally, blinded site personnel, not present at the index procedure, will be assigned to conduct the clinical follow-up and they will be provided with a standard follow-up interview in order to reduce bias and maintain subject blinding. Subject blinding should be maintained until the 5-year follow-up visit for all registered subjects is completed.

The physician performing the procedure will not be blinded to the assigned treatment. Thus, if clinical follow-up with a study physician is deemed necessary at the protocol required follow-up time points, a different physician (or designee) than the one who implanted the device(s) must conduct the follow-up clinical visits in order to maintain subject blinding. Similarly, follow-up visits with research personnel must be conducted by different persons than those who were unblinded during the index hospitalization. Site personnel will be adequately trained such that the physician (or designee) conducting the clinical follow-up is adequately blinded to the treatment received by the subject. For unscheduled visits, subjects may see the physician who

implanted the device(s). Treating physician should prevent unblinding of the subject when they conduct any non-protocol related visits. In addition, hospital notes, dictated notes, notes to referral physicians, billing information, and other related patient information must refer to the assigned treatment device as “study device” or other non-revealing language, to maintain the blind. The only exception to these requirements is if the hospital billing department does not allow this practice. Sites will be provided with a blinding guidance document that will instruct the sites on how to maintain blinding at the clinical sites.

The Clinical Events Committee (CEC) will be blinded to the randomization assignments. The angiographic core laboratories cannot be blinded to the device received. The Data Safety Monitoring Board (DSMB) will also be blinded to the subject’s randomization. Independent statisticians will generate blinded tables for review by the DSMB. The DSMB may request unblinded data if a safety signal is observed.

Sponsor personnel that will be unblinded will be the independent biostatisticians involved in generating and verifying the randomization code, key Clinical Science and Operations, Clinical Safety Monitors, Site Monitors, Clinical Data Management, Electronic Database Programmer, Inventory Management staff, and Clinical Information System (IS) personnel working on the trial. Restricted access of blinded personnel to the clinical database will be maintained until unblinding of the study.

#### ***4.5 Early Termination of the Clinical Trial***

Please refer to **section 4.6** of ABSORB III Protocol (Version 17.0, August 09, 2018) for the relevant information about trial early termination.

### **5. ENDPOINTS**

#### ***5.1 Primary Endpoints***

##### **TLF through 30-day, tested for non-inferiority against the control**

- This analysis will consist of ~2600 subjects in ABSORB IV.
- TLF is defined as composite of Cardiac Death, Myocardial Infarction (per protocol-defined MI definition, Appendix II) attributable to Target Vessel (TV-MI), or Ischemia-Driven Target Lesion Revascularization (ID-TLR).

#### ***5.2 ABSORB IV Major Secondary Endpoint***

- **TLF through 1-year, tested for non-inferiority against the control**
- **ABSORB IV Angina Powered Secondary Endpoint:** The percentage of patients who experienced angina within 1 year, tested first for non-inferiority with reflex to superiority against the control.
  - Angina is defined as any angina or angina equivalent symptoms determined by the physician and/or research coordinator after interview of the patient, and as adjudicated by a clinical events committee (CEC).

- This analysis will exclude angina or angina equivalent symptoms that occurred following the index procedure through hospital discharge or 7 days, whichever occurs first.
- This analysis will consist of ~2600 subjects in ABSORB IV.

### **5.3 Additional Secondary Endpoint(s)**

In ABSORB IV the following clinical secondary endpoints will be analyzed for all the ~2600 subjects.

- **Acute Success:** (Combined Clinical/Angiographic Endpoint)
  - Device success (Lesion level analysis)
  - Procedural success (Subject level analysis)
- **Clinical Endpoint** in hospital and at each follow-up point (30, 90, 180, 270 days; 1, 2, 3, 4, 5 years).
  - **Component**
    - Death (Cardiac, Vascular, Non-cardiovascular)
    - Myocardial Infarction
      - Attributable to target vessel (TV-MI)
      - Not attributable to target vessel (NTV-MI)
    - Target Lesion Revascularization (TLR)
      - Ischemia driven TLR (ID-TLR)
      - Non ID TLR (NID-TLR)
    - Target Vessel Revascularization (TVR,
      - ID TVR
      - Non ID TVR
    - All coronary revascularization
  - **Composite Endpoints**
    - Death/All MI
    - Cardiac Death/All MI

- Cardiac Death/TV-MI/ID-TLR (TLF)
- Cardiac Death/All MI/ID-TLR (MACE)
- Cardiac Death/All MI/ID-TLR/ID-TVR, non TL (Target Vessel Failure, TVF)
- Death/All MI/All revascularization
- **Scaffold-Thrombosis / Stent Thrombosis (per ARC definition)**
  - Timing (acute, sub-acute, late and very late)
  - Evidence (Definite and Probable)
- Rehospitalization
  - Coronary artery disease related
  - Cardiovascular, non-CAD related
  - Non-cardiovascular related
- Repeat coronary arteriography
- TLF through 5 years based on 4600 subjects (2000 primary analysis subjects of ABSORB III and 2600 subjects of ABSORB IV)

## 5.4 Informational Endpoints

### 5.4.1 Patient Reported Outcomes

Patient-reported outcomes are informational endpoints to assess Health-Related Quality of Life at baseline, 1, 6, 12 months and will be assessed at 3 and 5 years throughout the remaining duration of the trial. These PRO endpoints will be evaluated in the ~2600 subjects of ABSORB IV. The following questionnaires will be used in this study:

- Seattle Angina Questionnaire-7 (SAQ-7) to assess disease-specific Quality of Life
- EuroQoL 5D (EQ-5D) survey to assess overall health status

The PROs will be analyzed to evaluate the relationship between quality of life and cardiovascular events that occurs post-PCI and to substantiate the clinical impact of the angina events identified in the trial.

### 5.4.2 Health Economics

During the course of the trial, the Sponsor (or the health economic core laboratory) will collect health economic data. The data may include billing information and claims data for the index hospitalization and for subsequent hospitalizations during the follow-up period, for sites located in the United States only. Patients will be asked to provide consent to access billing information for the purposes of conducting economic analysis of the trial.

Additional information regarding medical resource utilization may also be collected throughout the trial, including but not limited to: laboratory services, diagnostic procedures, or pharmacy records.

## 6. SUBJECT SELECTION AND WITHDRAWAL

### 6.1 *Subject Population*

Subjects registered into this Clinical Investigation will be male and female subjects derived from the general interventional cardiology population. The Clinical Investigation will register approximately 2600 subjects, with up to three *de novo* native coronary artery lesions in a maximum of two epicardial vessels and a maximum of two lesions per epicardial vessel, who meet all eligibility criteria, have provided written Informed Consent and have been registered in the trial.

### 6.2 *Subject Screening and Informed Consent*

#### 6.2.1 *Subject Screening and Informed Consent*

Please refer to **section 6.2.1** and **6.2.2** of ABSORB III Protocol (Version 17.0, August 16, 2018) for the relevant information about subject screening and informed consent.

#### 6.3 *Eligibility Criteria*

Assessment for general eligibility criteria is based on the medical records of the site and interview with a candidate subject. Clinical and laboratory test of the eligibility assessment shall be per site standard of care. If some of the protocol required tests are not included in the site's standard tests, they must be done, but after written Informed Consent has been obtained. Subjects must meet ALL of the inclusion criteria to be considered for the clinical evaluation. If ANY of the exclusion criteria are met, the subject is excluded from the clinical evaluation and cannot be registered. Please see **Protocol Summary**, Inclusion Criteria and Exclusion Criteria, for details of the eligibility criteria of ABSORB IV.

#### 6.4 *Point of Registration*

During the randomization phase, the subject is considered randomized after IVRS has been called and a device has been assigned (Absorb BVS or XIENCE). The subject is considered registered and in the ITT population at the point of randomization. Once randomization is completed and a treatment arm is assigned, crossover is not permitted. Regardless of the actual device the subject received, the subject will be included in ITT population per the original randomization assignment.

Refer to **Appendix IV** and **Figures 1 and 2** for further registration details.

#### 6.5 *Subject Discontinuation*

Please refer to **section 6.5** of ABSORB III Protocol (Version 17.0, August 16, 2018) for the relevant information about subject discontinuation.

## 7. TREATMENT AND EVALUATION OF SAFETY AND EFFECTIVENESS

### 7.1 *Baseline*

#### 7.1.1 *Baseline Laboratory Assessments to Confirm Subject Eligibility*

Subject preparation will be in accordance with standard hospital policy for the care of interventional cardiology subjects.

#### 7.1.2 *Subject History*

Subject history will include demographics (e.g., age, gender), cardiac history including but not limited to Canadian Cardiovascular Society (CCS) and Braunwald classification of angina, history of myocardial infarction, diabetes mellitus, hypertension, hypercholesterolemia, previous CABG and PCI, and concomitant cardiovascular medications (Refer to **Appendix II** for Definitions). In addition, measurements of weight, height, and resting blood pressure will be collected.

#### 7.1.3 *Patient-Reported Outcomes Assessment*

All ~2600 subjects in ABSORB IV will complete the following Patient Reported Outcome questionnaires prior to the index procedure\*.

- EuroQoL 5D (EQ-5D) survey to assess overall health status.
- Seattle Angina Questionnaire-7 (SAQ-7) to assess disease-specific Quality of Life.

Please refer to **section 7.1.3** of ABSORB III protocol (Version 17.0, August 16, 2018) for the details regarding each questionnaire.

\*Every effort should be made to have subjects complete all three patient reported outcomes questionnaires prior to the procedure. However, in situations where this is absolutely not possible, subjects may complete them post-procedure, prior to discharge. Subjects who complete their questionnaires post-procedure should base their responses on their condition prior to the procedure.

### 7.2 *Pre-Procedure*

#### 7.2.1 *Pre-Procedure Laboratory Assessment*

The following laboratory assessments need to be obtained prior to the index procedure or at the time of the index procedure depending on the assessment and condition of the subject.

**Table 7.1** **Baseline Laboratory Assessment**

 Demographics include age, gender, post-menopausal status, date of birth, race/ethnicity, highest level of education, employment status and household income.

Within 21 days prior to procedure†	Within 7 days prior to procedure	Within 48 hours prior to procedure
Platelet and White Blood Count	Pregnancy test (if applicable)	12-lead ECG (within 24 hours preferred)
Hemoglobin		Creatine kinase (CK)
Serum Creatinine		Creatine kinase myocardial-band isoenzyme (CK-MB)
HbA1c‡		Troponin (if suspected acute coronary syndrome, within 24 hours)
Estimated GFR*		

†The 21-day lab results must be known prior to index procedure.

‡ HbA1c is to be collected in diabetic subjects only, and its result is not needed prior to the index procedure.

\* Glomerular Filtration Rate

The following applies to cardiac enzyme measurement pre-procedure and during the procedure.

- All patients admitted with the diagnosis of possible acute coronary syndrome (including unstable angina, NSTEMI or STEMI) must have at least one and preferably 2 or more complete sets of cardiac biomarkers ( a set consisting of troponin (I or T), CK and CK-MB) measured within 24 hours of procedure. Measurements should be at least 6 hours apart if multiple measurements were taken.
- If the patient has stable coronary artery disease or silent ischemia, a pre-procedure CK and CK-MB must be drawn, but may be obtained during the procedure from the arterial sheath but prior to any angioplasty. The angioplasty procedure may then be performed before the results are known.
- To assist in the determination of peri-procedural MI, during the procedure, all patients with an acute coronary syndrome (including unstable angina, NSTEMI or STEMI) must have troponin, CK and CK-MB drawn from the arterial sheath prior to first balloon inflation.

For subjects having staged procedures, the protocol-required pre-procedure and post-procedure cardiac enzyme and 12-lead ECG assessments must be repeated for the staged procedure in the same manner as done for the original index procedure.

### **7.2.2 Dual Anti-Platelet Medications**

Subjects selected for treatment with Absorb BVS or XIENCE must receive a loading dose of  $\geq$  300 mg of aspirin within 24 hours, regardless of whether the patient was previously taking aspirin. For patients undergoing staged procedure who have not been discharged and have been prescribed daily aspirin while in hospital, no aspirin reloading is required.

For patients with stable coronary symptoms, silent ischemia, or acute coronary syndromes in whom all measured troponin and CK-MB values were within normal limits, pre-loading with clopidogrel between 3 and 24 hours prior to the index procedure or prasugrel or ticagrelor between 1-24 hours prior to the index procedure is strongly recommended. If the above loading time periods are not possible, the P2Y12 inhibitor must be administered in all patients no later than 1 hour after the procedure. If the subject receives less than the required amount of the loading dose for a P2Y12 receptor inhibitor, the investigator is to give the remaining amount of the same agent in the next 24 hours and within the protocol required timeframe.

**Confidential and Proprietary**

**Do not distribute or reproduce without the prior written permission of Abbott Vascular Inc.**

**ABSORB III Randomized Control Trial Version 17.0 August 16, 2018.**

Note: The biomarker measurements in patients with stable coronary symptoms and silent ischemia may be pending at the time of the procedure, or may be drawn from the arterial sheath prior to first balloon inflation; such patients may still be randomized, and a P2Y12 receptor inhibitor must be administered no later than 1 hour after the procedure.

For patients with acute coronary syndromes in whom any troponin or CK-MB value at any time prior to the index hospitalization was elevated, one of two treatment options must be used a) a loading dose of clopidogrel between 3 and 24 hours prior to the procedure or prasugrel or ticagrelor between 1-24 hours prior to the index procedure must be given, OR b) an intravenous GP IIb/IIIa inhibitor or cangrelor (see below) must be administered prior to and/or during PCI but prior to first balloon inflation, per institution standard of care. If an intravenous GP IIb/IIIa inhibitor is given, a P2Y12 receptor inhibitor must be given within 1 hour following the index procedure. If intravenous cangrelor is used, the timing of the first administration of the P2Y12 receptor inhibitor should be as follows: clopidogrel or prasugrel are administered at the time of discontinuation of the cangrelor infusion; ticagrelor may be administered before, during, or immediately upon discontinuation of the cangrelor infusion. Ticagrelor is the preferred P2Y12 receptor inhibitor in cangrelor-treated patients. Cangrelor should be maintained 2-4 hours post procedure according to label.

Note: If the subject receives less than the required amount of the loading dose for a P2Y12 receptor inhibitor, the investigator is to give the remaining amount of the same agent in the next 24 hours and within the protocol required timeframe.

The protocol required loading dose may be omitted in a) stable CAD or ACS patients maintained on chronic P2Y12 receptor inhibitor for  $\geq$  7 days, and b) patients who received a P2Y12 receptor inhibitor loading dose 1-7 days prior to the procedure and who have been maintained on a daily dose since. However, it is strongly recommended that stable patients on chronic clopidogrel are reloaded with a P2Y12 receptor inhibitor. For ACS patients on chronic clopidogrel, they must be reloaded with a P2Y12 receptor inhibitor if they did not already receive a loading dose of clopidogrel, prasugrel, or ticagrelor in the 24 hours prior to the procedure.

Ticlopidine may be used as a substitute at a dose in accordance with standard hospital practice only if the subject develops hypersensitivity or intolerance to clopidogrel, prasugrel, or ticagrelor during the trial.

Refer to respective prescribing information for P2Y12 receptor inhibitor for further details regarding loading practice.

Cangrelor may be used pre-PCI at operator discretion as per local practice in any patient (but should be used similarly in patients randomized to ABSORB and XIENCE): a pre-PCI loading dose of 30  $\mu$ g/kg IV followed by an IV infusion of 4  $\mu$ g/kg for at least 2 hours and for a maximum of 4 hours may be used, in conjunction with an oral P2Y12 inhibitor. If ticagrelor is selected, the ticagrelor loading dose may be given before, during or immediately upon discontinuation of the cangrelor infusion. If clopidogrel or prasugrel are selected, a clopidogrel or prasugrel loading dose should be given immediately upon discontinuation of the cangrelor infusion, even if a loading dose was given earlier.

For subjects having staged procedures, the pre-procedure administration regimen of aspirin and P2Y12 receptor inhibitor (dosage requirements and timing) must be repeated prior to the staged

procedure in the same manner as done for the original index procedure. If the subject has not been discharged between the index and staged procedures, and has received daily aspirin while in hospital, no aspirin reloading is required (see above).

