Antiplatelet Therapy	
Antiplatelet Medication Loading Dose:
 

Aspirin: Subjects must receive a loading dose of <math>\geq 300</math> mg of aspirin within 24 hours before the procedure, regardless of whether the patient was previously taking aspirin. For patients undergoing staged procedure who have not been discharged and have been prescribed daily aspirin while in hospital, no aspirin reloading is required.

P2Y12 receptor inhibitors: either clopidogrel, prasugrel or ticagrelor may be used as per standard of care and per label indications.

Clopidogrel: a peri-procedural loading dose 600 mg is required

Prasugrel: a peri-procedural loading dose of 60 mg is required

Ticagrelor: a peri-procedural loading dose of 180 mg is required.

For patients with stable coronary symptoms, silent ischemia, or acute coronary syndromes in whom all measured troponin and CK-MB values were within normal limits, pre-loading with clopidogrel between 3 and 24 hours prior to the procedure or prasugrel or ticagrelor between 1-24 hours prior to the index procedure is strongly recommended. If the above loading time periods are not possible, a P2Y12 inhibitor must be administered in all patients no later than 1 hour after the procedure. If the subject receives less than the required amount of the loading dose for a P2Y12 receptor inhibitor, the investigator is to give the remaining amount of the same agent in the next 24 hours and within the protocol required timeframe.

 
Note: The biomarker measurements in patients with stable coronary symptoms and silent ischemia may be pending at the time of the procedure, or may be drawn from the arterial sheath prior to first balloon inflation; such patients may still be randomized, and a P2Y12 receptor inhibitor must be administered no later than 1 hour after the procedure.
 
For patients with acute coronary syndromes in whom any troponin or CK-MB value at any time prior to the index hospitalization was elevated, one of two options must be given a) a loading dose of

--	--

 ABSORB IV will allow the use of FDA approved P2Y12 inhibitors. Loading and maintenance dosages of all P2Y12 inhibitors should follow respective prescribing information. If outside the US, country specific approvals are allowed.

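### ABSORB IV's mandatory antiplatelet rule for biomarker-positive ACS is tied to values raised before hospitalization, almost certainly a slip for *procedure*, so patients first positive after admission fall outside it

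*Combined protocol and SAP*

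**What the plan says.** Section 7.2.2 (Dual Anti-Platelet Medications) of ABSORB IV sorts patients by their biomarkers before setting the P2Y12 loading rule.

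The first group is patients with stable symptoms, silent ischemia, or "acute coronary syndromes in whom all measured troponin and CK-MB values were within normal limits". For them a timed pre-load is strongly recommended. If it is not possible, "the P2Y12 inhibitor must be administered in all patients no later than 1 hour after the procedure".

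The second group is defined as "For patients with acute coronary syndromes in whom any troponin or CK-MB value at any time prior to the index hospitalization was elevated". For them one of two options is compulsory:

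- (a) clopidogrel 3 to 24 hours before the procedure, or prasugrel or ticagrelor 1 to 24 hours before it;
- (b) an intravenous GP IIb/IIIa inhibitor or cangrelor, started before the first balloon inflation.

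The Antiplatelet Therapy row of the ABSORB IV Protocol Summary has the same trigger and the same force: "at any time prior to the index hospitalization was elevated, one of two options must be given".

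**The concern.** The two groups read as if they were meant to cover every ACS patient: all values normal, or at least one raised. The time limit in the second definition breaks that. A patient who was normal or unmeasured before admission and first tests positive on the ward does not have all values normal, yet has none raised before hospitalization. Read literally, such a patient is in neither group.

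The literal rule also runs against risk. A patient whose markers rose before admission and have since settled must be covered, while a patient whose markers are rising in hospital need not be.

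What is at stake is a peri-procedural safety rule for patients receiving a scaffold or stent. Such a patient could be treated with neither a pre-load nor an intravenous agent at balloon inflation and still be within the protocol.

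**Working it through.** The plan gives no figure on this point and no arithmetic applies. The check compares the loading rules by the time of the first raised biomarker in an ACS patient.

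| First raised troponin or CK-MB | Group as written | Compulsory cover before first balloon inflation | Group if the word were *procedure* |
|---|---|---|---|
| Before the index hospitalization | Second | Yes: option (a) or (b) | Second |
| Never; all measured values normal | First | No; pre-load strongly recommended | First |
| After admission, before the procedure | Neither | No | Second |

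Changing the one word moves only the third row, and makes the two groups complementary for values obtained before the procedure.

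**Is it a slip?** Three features of the plan point to *procedure*.

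- The first group refers to all measured values, with no reference to admission.
- Section 7.2.1 and the Cardiac Biomarker Collection row of the Summary require at least one full biomarker set within 24 hours of the procedure in patients admitted with possible ACS. In-hospital values are therefore routine data.
- The general inclusion criteria date unstable angina and NSTEMI from the index procedure (within 2 weeks), not from admission.

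**Can such patients enter?** Yes. NSTEMI within 2 weeks is eligible, and the acute-infarction exclusion covers only STEMI within 72 hours. The MI definition in ABSORB IV Appendix II has a category for patients whose latest baseline CK-MB was still rising.

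**What still protects the third-row patient?**

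1. An oral P2Y12 inhibitor within 1 hour after the procedure (section 7.2.2). This comes after balloon inflation.
2. A compulsory reload for ACS patients on chronic clopidogrel who were not loaded in the preceding 24 hours (section 7.2.2). This covers a subset only.
3. Under unfractionated heparin, section 7.2.3 says biomarker-positive ACS patients should receive a GP IIb/IIIa inhibitor, with no limit on when the marker rose. This is advice, not a requirement.
4. Under bivalirudin, section 7.2.3 discourages routine GP IIb/IIIa use but makes an exception for an ACS patient who had no recommended pre-load and no cangrelor. This permits the drug without requiring it.
5. Section 7.2.2 leaves cangrelor to operator discretion in any patient.

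So under heparin the requirement becomes a recommendation, and under bivalirudin it becomes an option. Patients whom section 7.2.2 exempts from loading, because they are already on maintenance therapy or were loaded 1 to 7 days earlier, are outside this point.

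**The case against.** The best answer is that this is a wording slip that no experienced site would follow literally. The companion group shows the intent, and sections 4.4.1 and 7.2.3 speak of biomarker-positive ACS without any link to admission. Section 7.2.3 even anticipates the ACS patient on bivalirudin without a pre-load. A sample drawn before formal admission would also satisfy the literal trigger. Much of this stands: it limits the likely practical effect, and it is why the severity is low. It does not remove the point, because the same word appears in both statements of a compulsory rule and nothing elsewhere corrects it.

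A reader might also infer one of four stronger claims, which the documents do not support.

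- *The uncovered patient has a later oral-load deadline.* The 1-hour limit is stated for all patients, and the compulsory group has the same limit under one of its options: "If an intravenous GP IIb/IIIa inhibitor is given, a P2Y12 receptor inhibitor must be given within 1 hour following the index procedure". The loss is cover at balloon inflation, not oral timing.
- *Late arterial-sheath results in ACS leave a second hole.* It is true that "The biomarker measurements in patients with stable coronary symptoms and silent ischemia may be pending at the time of the procedure" names only stable patients and silent ischemia. But ACS patients must already have a set drawn within 24 hours, and section 7.2.1 gives the purpose of their sheath sample as helping to determine peri-procedural MI. It is not presented as a treatment trigger.
- *Biomarker-positive ACS needs a new definition for the stratification factor in section 4.4.1.* The slip in the loading rule does not establish that, and redefining a stratum in a running trial has costs of its own.
- *The comparison of devices is biased.* The rule is identical in both arms, and nothing in the documents suggests it is applied differently.

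**Conclusion.** The point holds as a low-severity correction to a safety rule. As written, ABSORB IV sets no compulsory choice between a pre-load and an intravenous agent for an ACS patient first biomarker-positive after admission. The gap matters mainly under bivalirudin, where nothing else requires cover at balloon inflation. It has no effect on alpha, power or the between-arm comparison.

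The documents do not say how many subjects are affected, and no estimate is offered. The conclusion rests on two readings. One is that the 1-hour oral deadline, stated for all patients, does reach the uncovered patient; if it were confined to its own paragraph, less protection would remain. The other is that *procedure* was intended, which is a strong inference but not stated. How sites read the rule in practice is not recorded.

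**What to change.** In section 7.2.2 of ABSORB IV and in the Antiplatelet Therapy row of its Protocol Summary, replace *hospitalization* with *procedure* in the trigger, and notify sites. If a positive result arrives too late for a timed pre-load, option (b) remains available, so the corrected rule is workable.

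The documents do not say outright whether enrolment has closed. If it has, add one descriptive table by arm showing P2Y12 load timing and intravenous agent use in ACS patients with any raised pre-procedure biomarker. This is a small extension of section 10.4.4, which already plans to relate thrombosis and bleeding events to antiplatelet therapy.

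The cost is one word in two places and a site notice, or one table. Endpoints, sample size and stratification do not change.
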